## **7.0 TRIAL DESIGN**

This is an open-label, non-randomized pharmacokinetic study of pre-surgical fulvestrant in women scheduled for mastectomy or lumpectomy. Eligible subjects will be identified upon admission to the institution for surgical management of breast cancer or DCIS, specifically mastectomy or lumpectomy. There will be 5 groups, each consisting of 6 subjects. The first subject of each group will receive fulvestrant administered intramuscularly and the next 5 subjects will receive fulvestrant intraductally. Subjects where at least 1 suitable duct is identified may undergo nipple aspiration in order to facilitate duct identification and

intraductal infusion of a fulvestrant accompanied by imaging (saline+ ultrasound). A maximum of 5 ducts will receive intraductal infusion of fulvestrant. Across all ducts, the total dose will not exceed 500 mg (10 mL). All subjects will be monitored for systemic and local adverse events during the procedure, immediately following the procedure, within 30 minutes, 1 hour, 4 hours and by phone following discharge on Days +1 and +2, +7, and pre-operative. Subsequent to mastectomy or lumpectomy, subjects will be assessed for systemic adverse events until discharge. Per schedule specified in Table 1, subjects will undergo serial blood draws to determine fulvestrant blood concentration levels.

When fulvestrant is administered at or below the dose level of 500 mg currently in routine clinical use, emergence of Dose Limiting Toxicities (DLT) is unlikely, but not impossible.

Since only a single instillation of fulvestrant is given in this protocol, dose reduction in individual subjects is not possible. However, if any of the DLT parameters reaches any of the thresholds values set in Section 10.3 the dose in subsequent subjects will be reduced to 250 mg (one 5 mL vial).

The purpose of this observational study is to understand the safety and tolerability of giving the anti-estrogen drug fulvestrant directly into the milk ducts of the breast, and collect any evidence of pathologic response. This study will be conducted under good clinical practice (GCP) guidelines as outlined in Section 15.5 Good Clinical Practice. This will be a single-dose study with two treatment groups: 500 mg administered intramuscularly (n=6) and up to 500 mg administered intraductally (n=24).

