## 8.0 SELECTION AND WITHDRAWAL OF SUBJECTS

This trial will enroll at least 30 eligible subjects for participation to result in 30 evaluable subjects.

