#### **8.4 Subject Discontinuation**

All subjects have the right to terminate participation in the study at any time. The Investigator also has the right to discontinue the subject's participation at any time

regardless of whether the subject wishes to continue in the study. The Sponsor may discontinue the study at anytime.

In addition, subjects may be withdrawn from the study for the following reasons:

- Occurrence of a clinically unacceptable AE
- Violation of the study protocol or lack of compliance with protocol regimens
- Subject declines further study participation
- Subject withdraws informed consent
- Investigator judges it is in the best interest of the subject

If a subject is withdrawn or discontinues study participation, reasonable efforts will be made to bring the subject in to complete the final study procedures. The subject will continue to be followed and medically managed in accordance with the arrangement that was in place prior to study enrollment. The reason(s) for a subject's discontinuation from the study are to be recorded in the source documentation and on the CRFs.

Any subject, who voluntarily or involuntarily withdraws from the study prior to mastectomy or lumpectomy, will be replaced.

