### 10.3 Dose Limiting Toxicity

If Dose Limiting Toxicities (DLT) are identified meeting the definition set forth below, the dose in subsequent subjects will be lowered to no more than 250 mg total (5 mL). DLT will include any study-drug related grade 5 toxicity (death). In addition, if 20% or more ( $\geq 6$  subjects) exhibit a single study drug-related Grade 3 or 4 adverse event (AE) per the CTCAE or SAE as defined in Section 11.2.3, the dose in subsequent subjects will be reduced to 250 mg. SAE Definition in the following categories: blood/bone marrow, cardiac, general constitutional symptoms, dermatology/skin, gastrointestinal, thrombo-embolic, hemorrhage/bleeding, infection, metabolic/laboratory, musculoskeletal/soft tissue, neurology, pain, pulmonary, upper respiratory, renal/genitourinary, or vascular this will be considered DLT and the study drug dose lowered for subsequent subjects. Additionally, if 50% or more subjects ( $\geq 15$  subjects), experience greater than 5 study related Grade 2 AE, this will be considered DLT and the study drug dose in subsequent subjects be lowered to 250 mg. Subjects who experience an allergic reaction, including anaphylaxis, to the dyes or drugs in this study will not be considered a DLT.

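### The dose-reduction counts in Section 10.3 (6 and 15) are fractions of all 30 planned subjects, and the text does not say whether the count or the percentage governs; read as counts, the rule often acts too late to lower anyone's dose.

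*Combined protocol and SAP*

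**What the plan says.** Section 10.3 has three triggers. Any drug-related death is one. The second applies "if 20% or more ( $\geq 6$ subjects) exhibit a single study drug-related Grade 3 or 4 adverse event (AE", with SAEs counted as well. The third applies "if 50% or more subjects ( $\geq 15$ subjects), experience greater than 5 study related Grade 2 AE". The consequence is the same each time: "the dose in subsequent subjects will be lowered to no more than 250 mg total (5 mL".

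Section 7.0 confirms that one threshold is enough: "if any of the DLT parameters reaches any of the thresholds values set in Section 10.3 the dose in subsequent subjects will be reduced". It adds that each subject is dosed only once, so no individual's dose can be cut after the event. Sections 7.0 and 9.1 plan five groups of six, each dosed as one intramuscular (IM) subject followed by five intraductal (ID) subjects.

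Section 8.0 gives the size: "This trial will enroll at least 30 eligible subjects for participation to result in 30 evaluable subjects". Section 8.4 adds: "Any subject, who voluntarily or involuntarily withdraws from the study prior to mastectomy or lumpectomy, will be replaced". No section gives a running denominator, a minimum number of subjects or a scheduled review for these triggers.

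**The concern.** A rule that can only help subjects not yet dosed has to be reachable while some remain. The two counts are set against the completed cohort instead. Safety and tolerability by a new route is the primary objective, and Section 11.2.1 accepts that side effects may differ in severity or frequency when the drug goes into the breast. Section 10.3 is the only place that fixes when the cohort's dose comes down.

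The pairing of a percentage with a count also leaves two readings that lead to different decisions for most of the trial. On one, a high early toxicity rate goes unanswered. On the other, a single early event changes the dose.

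**Working it through.** **1. Where the counts come from.** 0.20 × 30 = 6 and 0.50 × 30 = 15, as stated. With the 24 ID subjects as the base they would be 4.8 (so 5) and 12. The base is therefore all 30 subjects, both routes pooled.

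**2. The two readings compared.** The smallest whole number reaching 20% of n is 0.2n rounded up: 3 at n = 12, 4 at 18, 5 at 24. It first equals 6 at n = 26. For 50% it is 6, 9 and 12 at the same points, and first equals 15 at n = 29. The readings disagree up to subject 25 (Grade 3/4) and subject 28 (Grade 2).

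**3. If the count governs: observed rates.** Six events are 6/12 = 50%, 6/18 = 33%, 6/24 = 25% or 6/30 = 20%, leaving 18, 12, 6 or 0 planned subjects. Five of the first 10 with Grade 3/4 toxicity (50%) trigger nothing. The Grade 2 clause cannot act before subject 15, even if all of the first 14 qualify.

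**4. If the count governs: true rates.** To leave someone to protect, the count must be reached among the first 29 subjects. In the planned order IM subjects are numbers 1, 7, 13, 19 and 25, so the first 29 hold 5 IM and 24 ID. Pairs below are events in ID subjects only / rate shared by IM and ID.
- Grade 3/4 at 20%: P(Bin(24, 0.20) ≥ 6) = 0.344 / P(Bin(29, 0.20) ≥ 6) = 0.537.
- Grade 2 at 50%: P(Bin(24, 0.50) ≥ 15) = 0.154 / P(Bin(29, 0.50) ≥ 15) = 0.500.

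With a shared rate, the expected trigger point is 6/0.20 = 30 and 15/0.50 = 30. On average 4.3 and 2.2 subjects would be left for the lower dose.

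The group scheme gives 5 IM + 25 ID, but the Synopsis, Section 7.0 and Section 13.2 state 6 + 24. With 6 + 24 and an ID subject dosed last, the first 29 hold 23 ID, and the ID-only figures fall to 0.305 and 0.105. The shared figures do not change.

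**5. If the percentage governs.** 1/5 = 20%, so one event among the first five subjects is enough. Taken literally, so is one event in the first subject (1/1).

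**6. Same percentages on subjects dosed to date.** The example is 3 of 12, 4 of 18, 5 of 24, plus 6 at any time; for Grade 2, 6 of 12, 9 of 18, 12 of 24, plus 15 at any time. The number of events is carried forward subject by subject in the planned order, and the trial is removed once a boundary is met. The table gives the probability of acting before subject 30.

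| Clause and true rate | Present count | Example table |
|---|---|---|
| Grade 3/4, 5% | 0.001 / 0.003 | 0.01 / 0.03 |
| Grade 3/4, 10% | 0.03 / 0.06 | 0.10 / 0.17 |
| Grade 3/4, 20% | 0.34 / 0.54 | 0.51 / 0.68 |
| Grade 3/4, 30% | 0.77 / 0.91 | 0.86 / 0.94 |
| Grade 2, 50% | 0.15 / 0.50 | 0.46 / 0.75 |

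At 30% the larger difference is in timing. The mean number treated at full dose is 23.0/19.6 under the count and 16.8/14.6 under the table. With a first look at 18 instead of 12, the 10% row becomes 0.07/0.13 and the mean at 30% becomes 20.2/17.8.

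**7. Reporting delay.** If events in the latest five subjects are not yet known, at 30% the count acts with probability 0.584/0.771 and the table with backstop 0.643/0.825. The gain is smaller but in the same direction.

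**The case against.** A reader might infer that the triggers can be met only once nobody is left to dose. The documents do not support that. It holds for an observed rate of exactly 20% or 50% with the count governing. At those true rates up to about half of trials reach the count earlier, and higher rates reach it sooner still. Replacements may also be dosed after subject 30, and a related death acts at once.

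Nor does the trial lack safety oversight. Section 11.2.6 requires SAEs to reach the medical monitor within 24 hours, and Section 11.2.5 counts every Grade 4 and prolonged Grade 3 event as an SAE. Sections 15.3 and 15.4 let the sponsor stop the trial or close the site for safety. Section 9.11 stops treatment of further ducts for severe pain. These safeguards are discretionary or protect one subject; none sets a threshold for lowering the cohort's dose.

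Section 7.0 regards dose-limiting toxicity as unlikely at or below the routine dose. That is fair, but the routine experience is intramuscular.

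The strongest objection is that the percentage may govern, in which case 5 of 10 does trigger the rule. This stands, and it is why the defect is the unstated choice between the readings. That reading then needs a minimum number.

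The example table is also a compromise. With a minimum of 12, 5 of 10 still waits for subject 12 or a sixth event. At a true 20% the table fails to act in 1 − 0.51 = 0.49 or 1 − 0.68 = 0.32 of trials. Looks at group ends can act later than an unrestricted running percentage would.

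**Conclusion.** The concern holds in this form: Section 10.3 leaves open which of two thresholds governs, and neither works well as written. As counts, they are met in time in only 0.34 to 0.54 of trials at the 20% rate, and 0.15 to 0.50 at the 50% rate, that the protocol itself names as dose limiting. As a running percentage, the rule has no floor.

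The figures assume independent subjects, a constant rate, five groups of 1 IM + 5 ID, no replacements, and events known before the next subject is dosed. The rate means the share of subjects who qualify under the clause. If the words about a single Grade 3 or 4 event mean the same event across subjects, that share is smaller and the count acts less often. It should be fixed: the amendment is small and bears on the primary objective.

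**What to change.** Amend Section 10.3 to say that the percentages apply to subjects dosed to date, using events known before the next subject is dosed, from a stated minimum number. For example:
- Related Grade 3/4 AE or SAE (keep the SAE limb): 3 of 12, 4 of 18, 5 of 24, and 6 at any time.
- Grade 2 clause: 6 of 12, 9 of 18, 12 of 24, and 15 at any time.

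The at-any-time lines mean that the rule never acts later than the present counts. The minimum (12 or 18) is the sponsor's choice. Print the trigger probabilities beside the table. If the sponsor prefers the fixed counts alone, the section should say so and print theirs.

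The cost is one paragraph and a small table, with no added subjects or procedures. The downside is more reductions when toxicity is low: at a true 10% rate, 0.10/0.17 against 0.03/0.06 now, or 0.07/0.13 with a first look at 18. A reduction also leaves fewer subjects at the 500 mg limit for the Ki67 and PK summaries.

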## 11.0 ASSESSMENT OF SAFETY

This trial will use the descriptions and grading scales from the CTCAE v. 5.0 of the NCI for adverse event reporting. Information about all adverse events (AE), regardless of source (self-reported by subject, reported by questionnaire, collected through examination, laboratory or imaging) will be recorded in the medical record as well as CRF. The section below describes the procedures for collecting and reporting AE.

### 11.1 Procedures in Case of Emergency

The investigator is responsible for assuring that equipment, procedures and personnel with the expertise to manage medical emergencies are in place throughout the course of the study.

An emergency may constitute a serious adverse event (SAE), see Section 11.2.3 SAE Definition. In such case, the procedures outlined in Section 11.2.6 Procedures for Adverse Event Reporting for the should be followed.

### 11.2 Safety Monitoring and Reporting

#### 11.2.1 Adverse Events

Both signs and symptoms of local (breast and chest wall) and systemic toxicity will be evaluated.

The most common side effects of fulvestrant when given into the muscle in the buttocks, reported from previous studies and after marketing, include:

- nausea (14%)
  - injection site pain (12%)
  - back pain (11%)
  - bone pain (9%)
  - headache (8%)
  - joint pain (8%)
  - pain in extremities (7%)
  - hot flash (7%)
  - weakness (6%)
  - vomiting (6%)

- loss of appetite (6%)
- muscle pain (6%)
- constipation (5%)
- cough (5%)
- shortness of breath (5%)

Increased liver enzymes (which may indicate liver damage) and allergic reaction may also occur, but in less than 5% of patients who receive the drug.

All of the side effects listed above may occur, but may or may not be the same in severity or frequency when fulvestrant is injected into the breast.

There are additional possible discomforts or risks from administration into the breast, as that process includes administration of anesthetic, breast duct identification using the aspirator, catheter placement and fulvestrant injection. These additional risks include:

- injury to the milk duct
- bleeding and bruising
- infection
- breast pain, discomfort or inflammation
- allergic reaction to the anesthetic, ~~eyes~~, or the study drug, fulvestrant, used in this study.

### 11.2.2 Adverse Event (AE) Definition

An adverse event (AE) is defined by the NCI as any unfavorable symptom, sign, or disease (including an abnormal laboratory finding) associated with the use of a medical treatment, device or procedure that may or may not be considered related to or caused by the medical treatment or procedure. An AE also includes any newly occurring event or previous condition that has increased in severity or frequency since the initiation of the investigational procedures or administration of the investigational drug or device.

Assessment of the occurrence of an AE will be based on changes in the subject's laboratory results and/or signs and symptoms. AEs will be monitored until they are resolved or clearly determined to be due to a subject's stable or chronic condition or concurrent illness (es). Medical care will be provided, as defined in the informed consent, for any AE.

Collect all Adverse Events on the Adverse Event (AE) CRF and the MedWatch 3500 form. There are two types of adverse events, expected and unexpected. It is expected that subjects may feel slight minimal discomfort during the study procedures and post-procedure; both events are considered self-limiting. It is further expected that subjects will experience post-operative discomfort after surgery. This will be treated according to routine institution and clinician routine. Subjects who experience any untoward or unexpected after-effects following the study procedures, blood collection or surgery are instructed to contact the Principal Investigator or study coordinator immediately.

All AEs, regardless of intensity or causal relationship, are to be recorded in the CRF and source documentation. The investigator must determine both the intensity of the AE and the event's relationship to study product administration. Unexpected events such as excessive

discomfort or prolonged breast pain following the procedure, infection, persistent discharge, or any other condition reported by the subject and treated by a physician should be reported on the AECRF.

### 11.2.3 AE Intensity Classification

Intensity will be defined according to the following CTCAE criteria:

Grade	Definition
1	Mild AE
2	Moderate AE
3	Severe and undesirable AE
4	Life-threatening or disabling AE
5	Death related to AE

### 11.2.4 AE Relationship Classification

Assess the relationship to study interventions (investigational product or device) as follows:

Relationship	Attribution	Description
Unrelated to investigational agent/intervention	Unrelated	The AE is clearly NOT related to the intervention
	Unlikely	The AE is doubtfully related to the intervention
Related to investigational agent/intervention	Possible	The AE may be related to the intervention
	Probable	The AE is likely related to the intervention
	Definite	The AE is clearly related to the intervention

### 11.2.5 SAE Definition

An SAE is any untoward medical occurrence that is a prolonged Grade 3 AE or any Grade 4 or 5 event as defined above or:

- Results in death
- Is life threatening (refers to an event in which the subject was at immediate risk of death at the time of the event; it does not refer to an event which hypothetically might have caused death if it were more severe)
- New or prolongs existing hospitalization
- Results in persistent or significant disability/incapacity
- Is a congenital anomaly/birth defect
- Requires intervention to prevent permanent impairment/damage (Devices only)

A medical event that may not be immediately life threatening or result in death or hospitalization but may jeopardize the subject or may require intervention to prevent a serious outcome may also be considered serious. Medical and scientific judgment must be exercised when classifying events as serious.

A distinction must be drawn between SAEs and severe AEs. A severe adverse event is a major event of its type. A severe adverse event need not necessarily be considered serious. For example, nausea, which persists for several hours, may be considered severe nausea but does not fulfill the criteria for an SAE. Alternatively, a stroke, which results in only a

limited degree of disability, may be considered to be a mild stroke but would fulfill the criteria for an SAE.

***Monitor all SAEs until the event is considered resolved.***

All SAEs, regardless of relationship to study procedures, must be reported to the study medical monitor and reported according to the procedures outlined in Section 7.2.6 11.2.6 Procedures for Adverse Event Reporting.

**11.2.6 Procedures for Adverse Event Reporting**

An adverse event that fulfills any one or more of the criteria in Section 11.2.5 SAE Definition must be reported as an SAE according to the following guidelines:

The investigator must inform the Atossa medical monitor within 24 hours of learning of event by telephone, text or fax of any SAE which occurs during the course of each subject's study participation (e.g., from enrollment through study termination), whether or not considered causally related to the study procedure.

## **12.0 ACCOUNTABILITY, RISKS AND BENEFITS**

### **12.1 Accountability**

Accurate records must be maintained for all investigational devices received, dispensed, and returned or destroyed. The study drug, fulvestrant, will be purchased by the hospital pharmacy. The allocation and administration of study drug to the study participants must be fully and contemporaneously recorded. The site will maintain study drug, FullCYTE Breast Aspirator and Microcatheter supplies accountability during the study on accountability logs provided by the sponsor (or the site's form is acceptable and if the following information is collected: the identification of the subject to whom the drug or microcatheters were dispensed and the date, lot number and quantity of the drug dispensed to the subject. Unused study supplies will be returned to the Sponsor. The Sponsor or designee will conduct drug accountability during the course of the study and at site closeout. Disposition of unused study drug will be handled according to institutional standards. The Sponsor or designee will conduct final study supplies accountability at site closure.

## **13.0 STATISTICS**

The primary aim of this study is to assess safety and tolerability in subjects receiving intraductal fulvestrant. In addition, this trial aims to characterize the PK of this alternative route of administration, and compare the intraductal PK profile to that of standard intramuscular administration. A pharmacokinetic population analysis will be used to characterize biodiversity in exposure and alternative route absorption rate.

Additional analyses not described in the sections below may be specified in a Statistical Analysis Plan. A detailed Statistical Analysis Plan will be done prior to database lock.

### **13.1 Adverse Events Analysis**

All serious adverse events will be reported. All non-serious AEs occurring in at least 10% of the subjects will similarly be reported.

### **13.2 Sample Size and Statistical Analyses**

A total of 30 subjects who are undergoing mastectomy or lumpectomy will be included in this study: 6 will receive intramuscular, and 24 will receive intraductal fulvestrant. With respect to the sample size for the latter group with 24 subjects, it will be possible to detect an effect size of approximately 0.60 with 80% power and 0.69 with 90% power. Both of these are in the medium to large range according to Cohen's terminology and are based on the demonstration of a reduction in the Ki67 labeling index mean from baseline (diagnostic biopsy) to week 4 (surgically excised specimen) using a paired t-test. With these effect sizes and an anticipated 50% decline in the mean index, then the expectation would be a standard deviation in this reduction of about  $\pm 83.7\%$  for 80% power and  $\pm 72.3\%$  for 90% power.

The primary endpoint of this study is to assess safety and tolerability as measured by adverse events, subject pain assessment as well as signs of topical irritation seen on the excised specimen. In addition, the effect of the administration will be evaluated with respect to the change in Ki67 labeling index (primary efficacy endpoint) and changes in estrogen and progesterone receptor expression (secondary efficacy endpoints)

Descriptive statistics will be used to summarize the data (means/medians and standard deviations/interquartile ranges for quantitative data and proportions/percentages for categorical data such as adverse events), and numerically compare the groups with entry diagnoses of invasive ductal carcinoma and DCIS, respectively. In addition, the 6 study subjects who receive intramuscular fulvestrant will be qualitatively compared with the main study cohort of 24 subjects who receive intraductal fulvestrant.

The primary analysis of the change in Ki67 labeling index will be compared between the two time points (baseline or time of diagnostic biopsy versus 4 weeks or time of the surgically excised specimen collection) using the paired t-test (assuming normality of the differences) or the Wilcoxon signed rank test if normality cannot be demonstrated or a transformation to normality using the Box-Cox family of power transformations cannot be used. A similar analysis will be employed to evaluate the secondary endpoint of changes in mean estrogen receptor and progesterone receptor expression. In addition, 95% confidence intervals for the mean difference for these variables between the two time points will be computed using the t-statistic or a rank statistic as required by the distribution of the study data.

The results for the efficacy endpoints will be compared in a descriptive fashion with those seen by Kuter et al (Kuter I, Gee JMW, Hegg R et al): Dose-dependent change in biomarkers during neoadjuvant endocrine therapy with fulvestrant: results from NEWEST, a randomized Phase II study. *Breast Cancer Res Treat* 133: 237-246, 2012.

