### **5.1 Intraductal Doses of Cytotoxic versus Endocrine Agents**

Most cytotoxic agents are given based upon BSA, whereas endocrine agents such as fulvestrant or tamoxifen are not.

Consequently, the dose used in this study will not be tailored to BSA or body weight. The maximum dose of 500 mg selected for the study is based on US labeled Intra-Muscular (IM) dose. Since milk ducts differ in size and volume, it may not be possible to administer 500 mg (10 mL) in all subjects.

It is possible, but unlikely, that peak plasma concentrations of a dose given intraductally will reach the same level as the same dose given intramuscularly (IM). This is because the agent must diffuse out of the ducts to reach the bloodstream. Eventually the entire dose will be taken up systemically but it will happen over a longer period of time (the peak plasma concentration will be lower but the area under curve [AUC] should be the same). Hence it was decided that the total amount of drug given in a single intraductal installation would not be higher than the typical IM dose of fulvestrant. There will be 5 groups, each consisting of 6 subjects. The first subject of each group will receive fulvestrant administered intramuscularly and the next 5 subjects will receive fulvestrant intraductally.

A maximum of two 5 mL vials, each containing 250 mg fulvestrant may be delivered into one duct or distributed among up to five ducts targeted for intraductal instillation. Ductal systems range in shape, size and volume just as breasts range in shape and size. As noted before, there are a range of ducts (from 5-9) and each duct within a breast is a different size. The ductal systems have the capacity to accommodate a significant amount of fluid. In a breast feeding woman, a single breast can accommodate anywhere from 47.2 mL to 62.8 mL. In a non-lactating woman, it is estimated that each breast duct can be distended with as little as 1 mL and may accommodate up to 20 mL without perforation and only mild discomfort. Based on prior experience with intraductal therapy it was determined that no

single breast would be administered > 10 mL of fulvestrant, to be divided among up to 5 ducts targeted for instillation. This amount, in a non-lactating subject, would limit the risk of perforation and discomfort associated with intraductal instillation.

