## 9.0 TREATMENT OF SUBJECTS

### 9.1 Study Related Procedures

After each subject has reviewed and signed the informed consent, she will be enrolled in the study and assigned a study number as outlined below in Section 17.3 Data Collection Requirements. Further testing maybe necessary to determine eligibility and will commence upon enrollment. These tests are included in Section 9.2 Baseline Assessment. Some of the exams, tests or procedures may be a part of routine care for breast cancer and may be used as baseline assessments if conducted no more than 2 weeks prior to participation in the study. Other tests are only being done for the purpose of the study. A member of the study staff will go over, in detail, with each subject the tests that are being done specifically for the study and those that are considered routine care.

All subjects will receive fulvestrant, but the actual total dose received may vary within subjects receiving fulvestrant intraductally, as it is guided by the number of accessible ducts and volume of the ducts.

The first subject of each group will receive intramuscular (IM) fulvestrant (500 mg) and the next five subjects of that group will receive intraductal (ID) fulvestrant up to 500 mg. There are five groups, for a total of 30 subjects. After fulvestrant instillation, both signs and symptoms of local (breast and chest wall) and systemic toxicity will be evaluated using the CTCAE v. 5.0. Each Group – IM; ID, ID, ID, ID, ID.

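### The enrolment scheme gives 5 intramuscular and 25 intraductal subjects, but the stated arm sizes are 6 and 24, and the power statement uses 24

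*Combined protocol and SAP*

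**What the plan says.** The combined protocol and SAP gives two versions of the split between routes.

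**The enrolment scheme.** Section 5.1 says "There will be 5 groups, each consisting of 6 subjects". Section 7.0 repeats this and adds: "The first subject of each group will receive fulvestrant administered intramuscularly and the next 5 subjects will receive fulvestrant intraductally". Section 9.1 says that after the first, intramuscular (IM) subject, "the next five subjects of that group will receive intraductal (ID) fulvestrant up to 500 mg", and that "There are five groups, for a total of 30 subjects". It also prints the within-group sequence as one IM followed by five intraductal (ID) entries. Section 9.3.1 assigns IM treatment to the first subject of each group, and Section 9.3.2 assigns ID treatment to the second through sixth subject of each of five groups.

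**The stated arm sizes.** The synopsis (Section 2.0) lists 6 IM and 24 ID subjects. Section 7.0 closes with two treatment groups, "500 mg administered intramuscularly (n=6) and up to 500 mg administered intraductally (n=24"), so that section contains both versions. Section 13.2 opens its sample-size text with "6 will receive intramuscular, and 24 will receive intraductal fulvestrant", introduces the power calculation with "With respect to the sample size for the latter group with 24 subjects", and later plans that "the 6 study subjects who receive intramuscular fulvestrant will be qualitatively compared with the main study cohort of 24 subjects" treated intraductally.

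**The concern.** The study is not randomized, so position in the enrolment order is the allocation rule. A site that follows Section 9 cannot reach the arm sizes in Section 13.2. A site that aims for 6 and 24 must break the written sequence, and nothing says which subject's route should change.

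Three things depend on the answer:

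- the number of ID subjects behind the Ki67 power statement;
- the size of the IM group, which the synopsis makes the reference for Ki67 response and PK values, and which Section 6.2(b) and the opening of Section 13.0 use for the PK comparison between routes;
- the denominators that the later, more detailed SAP announced in Section 13.0 would inherit.

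**Working it through.** **1. Count the subjects.** Inputs: five groups, each with 1 IM then 5 ID (Sections 5.1, 7.0, 9.1, 9.3.2).

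- IM: 5 × 1 = 5, at enrolment positions 1, 7, 13, 19 and 25.
- ID: 5 × 5 = 25.
- Total: 5 + 25 = 30.

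Other numbers of groups do not help. Four groups give 4 IM and 20 ID (24 in all); six give 6 IM and 30 ID (36 in all). Six groups of 1 IM and 4 ID would give 6 IM and 24 ID, total 30, but no section describes that scheme.

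**2. Look for a rule that bridges the two.** Section 8.4 replaces subjects who withdraw before surgery. That restores numbers but does not move a subject from ID to IM. Section 8.0 fixes 30 evaluable subjects and says nothing about the split.

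**3. Reproduce the plan's power figures at n = 24.** Inputs from Section 13.2: paired t-test, effect sizes of about 0.60 (80% power) and 0.69 (90% power), anticipated decline of 50%, standard deviations of 83.7% and 72.3%. Alpha and sidedness are not stated.

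- Power = P(|T| > t(0.975, n − 1)), where T is noncentral t with n − 1 degrees of freedom and noncentrality d√n.
- SD = 50 / d.

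With n = 24 and two-sided 5%, d = 0.5972 and 0.6911. Then 50 / 0.5972 = 83.7 and 50 / 0.6911 = 72.3, which match the printed values. One-sided 5% gives d = 0.523 and 0.616 (SDs of 95.6 and 81.2). The two-sided normal approximation gives d = 0.572 and 0.662. Neither matches. Two-sided 5% is therefore the inferred setting, and it agrees with the 95% intervals planned in Section 13.2. The printed figures are correct for 24 subjects.

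**4. Repeat with the n that the scheme gives.**

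| Quantity | n = 24 (stated) | n = 25 (scheme) |
|---|---|---|
| Detectable d, 80% power | 0.597 | 0.584 |
| Detectable d, 90% power | 0.691 | 0.676 |
| SD for a 50% decline, 80% power | 83.7% | 85.6% |
| SD for a 50% decline, 90% power | 72.3% | 74.0% |
| Power at d = 0.60 | 80.4% | 82.1% |
| Power at d = 0.69 | 89.9% | 91.1% |

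**5. Check what else depends on the split.** The dose-limiting toxicity counts in Section 10.3 (6 subjects for 20%, 15 for 50%) use the total: 0.20 × 30 = 6 and 0.50 × 30 = 15. They do not change. Section 11.2.6 bases the safety analyses on subjects who received ID administration, so that planned set is 25 rather than 24.

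**The case against.** The best reply is that nothing of statistical substance changes. The power statement is right for 24 and slightly conservative for 25, and 0.584 is close to the plan's approximate 0.60. The IM group loses one subject in a comparison that Section 13.2 calls qualitative, with no test or interval attached. The total, the toxicity thresholds and the analysis methods are the same under either version.

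That is accurate as to size, and no loss of planned precision is claimed here. It does not resolve the contradiction. Each version appears in several sections, and the scheme is given in words, in numerals and as a printed sequence, so this is not one mistyped digit.

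Two further cautions stand. First, it is an inference that a site would enrol 5 and 25: Section 9 points that way, but the site also holds the synopsis and Section 7.0. Second, counting edits does not show which split was intended, and the documents do not say who has been enrolled. Either correction must agree with the routes already given. If six subjects have had IM treatment, a 5/25 statement would be false. If groups of six have been filled, a scheme of six groups of five can no longer describe the study.

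**Conclusion.** The concern holds. The written scheme gives 5 IM and 25 ID subjects, and the synopsis, the end of Section 7.0 and Section 13.2 state 6 and 24. This part is a count and needs no assumption beyond following the scheme as written.

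The consequence is modest. The IM reference group is one subject (one-sixth) smaller than stated. The ID group is one larger, which raises power by 1.7 percentage points at d = 0.60 (82.1 − 80.4) and by 1.2 at d = 0.69 (91.1 − 89.9). These power figures assume a two-sided 5% paired t-test, inferred because it reproduces the plan's numbers. The primary safety analysis is affected only by the one extra ID subject. It should be fixed because the allocation rule and the sample-size section contradict each other, not because power is at risk.

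**What to change.** Reconcile the passages to one version, after checking which routes have already been given.

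- **If the scheme stands (5 IM, 25 ID):** change the arm sizes in the synopsis, the last sentence of Section 7.0 and all three places in Section 13.2 (the opening sentence, the power statement and the qualitative comparison). Restate the detectable effect sizes as about 0.58 (80% power) and 0.68 (90% power), with standard deviations of about 85.6% and 74.0%. This touches three sections.
- **If 6 IM and 24 ID is intended:** describe six groups of five, one IM then four ID. Sections 5.1 and 7.0 need the number of groups, the group size and the count of ID subjects changed. Section 9.1 needs the same counts and a printed sequence with four ID entries. Section 9.3.2 needs second through fifth subject and six groups. Section 9.3.1 and the power figures stay as they are. This touches four sections and works only if groups of six have not already been enrolled.

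In either case, Section 13.2 should state the alpha and sidedness behind the power figures.

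No subjects are added. The cost is a signed amendment (Section 15.2) and IRB handling. Section 15.6 requires prior written approval but excepts purely logistical or administrative changes and allows expedited review of minor ones; Section 16.0 is stricter. Whether the consent form needs revision cannot be judged, because the consent pages are not in the public document.
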